Following successful completion of Phase 1, we will proceed with Phase 2 of the study. The aims of this phase will be:

- 1. Assess the sensitivity and specificity of a panel of DNA methylation markers in the nonendoscopic detection of BE using a capsule sponge device.
- 2. Assess the sensitivity and specificity of a panel of DNA methylation markers in the nonendoscopic detection of BE related dysplasia/carcinoma using a capsule sponge device.
- 3. Estimate the degree of missed dysplasia during routine surveillance endoscopy with random endoscopic biopsies, by utilizing follow up intensive endoscopic surveillance and capsule sponge examination.
- 4. Explore the utility of demographic, anthropometric and circulating biomarker risk factors in predicting the presence of BE and BE related dysplasia.

The inclusion and exclusion criteria, study procedures and biomarker assays will be identical to those described in Phase 1. All subjects will undergo the capsule sponge assessment followed by the clinically indicated endoscopy as described in Phase 1. All studies will be conducted using a single size sponge with the same porosity configuration selected from Phase 1. Study procedures, testing and follow up will be similar to that in Phase 1. Recruitment will be monitored and a future interim analysis may be conducted.

In addition to Mayo Clinic Rochester, subjects will also be recruited at Mayo Clinic Jacksonville; Mayo Clinic Arizona; Mayo Clinic Health Systems – Austin; Mayo Clinic Health Systems – Mankato; Northwell Health in Manhasset, NY; and Baylor University Medical Center in Dallas, TX. Enrollment is closed at University of Colorado, Denver – Anschutz Medical Campus in Aurora, CO.

[name] will be site PI at Mayo Clinic Jacksonville. [name] will be site PI at Mayo Clinic Arizona. [name], MD will be the site PI at Mayo Clinic Health Systems – Austin. [name] will be the site PI at Mayo Clinic Health Systems – Mankato. [name] will be site PI at Northwell Health. [name] will be the site PI at Baylor University Medical Center.

Preliminary Data:

Identification and initial feasibility testing of methylated DNA markers for BE diagnosis.

We aimed to prospectively assess the accuracy of methylated BMP3 and NDRG4 to identify BE using endoscopic biopsies (Phase 1) and brushings from the whole esophagus and cardia to simulate non-endoscopic sampling devices (Phase 2).

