A factorial design will be used to compare porosity of sponge 25 mm 10 pores per inch (PPI) vs. 25 mm 20 PPI, and Barrett's Esophagus vs. normal esophagus. Tolerability will be measured using a tolerability score as well as level of mucosal abrasion (scale 0-6, 6=worst). The assumed standard deviation for the tolerability score of 2.2 was obtained from Sami, et al.. Using a two-sided test of significance of 5% and 80% power, we can detect a minimal shift in tolerability score of at least 2. For mucosal abrasion score, a rough estimate of 1 standard deviation (s.d. ≈ range of data / 4) will be used and assuming a two-sided test of significance of 5% we have 86% power to detect a difference in mean mucosal abrasion score of at least 1. DNA yield will be measured using wild type Beta-actin. Using a two-sided test of significance of 5% we have 82% power to detect a fold change difference of 50%. All above power calculations are based on detection of main effect comparisons with n=20 per group. The ability to detect interactions between main effects will be very limited with the given sample size. Recruitment will continue until 40 individuals have successfully completed the sponge procedure using the

25 mm sponge. We anticipate 25% will decline swallowing sponges after they have consented, therefore the total number of people we anticipate recruiting will be set at 60.

Phase 2: For the detection of Barrett's Esophagus, sample size justification will be based on minimizing the width of the 95% confidence interval of the sensitivity for detecting Barrett's Esophagus with a fixed specificity of 90%. From table 2 below, based on various assumed sensitivities, the largest confidence interval width for the proposed sample size is less than ±9%. Similarly for detection of dysplasia among Barrett's Esophagus patients, the largest width for the proposed sample size is less than ±12. These confidence widths are reasonable for this initial feasibility study. We also intend to perform multivariable modeling using machine learning techniques to evaluate a minimum of 14 methylation markers. Using the rule of thumb for machine learning of 10-15 events per marker, a minimum of 140 to 210 cases and an equal number of controls is required (total 280 to 420 patients) to account for assay failures and indeterminate histological findings on endoscopic exam. We anticipate enrolling up to 1000 participants.

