In addition, clinically archived FFPE tissue from up to 10 cases will be used to assess methylated DNA marker levels in biopsies versus the sponge.

Due to the known dysplasia miss rate with routine surveillance endoscopy, we hypothesize that there will be undetected or missed dysplasia in BE patients with a negative surveillance histology. This imperfection in the endoscopic "gold" standard will bias the resulting accuracy estimates of methylation markers in a multitude of ways. There are several approaches in the literature to address this issue; all with their own caveats. The three approaches that will be investigated are latent class analysis, Bayesian estimation, and discrepant resolution. We have hence inflated the sample size estimates in table 2 to correspond with a 30% prevalence of undetected dysplasia in those with no dysplasia on conventional surveillance endoscopy to ensure that we have 50 true BE subjects without dysplasia.

Table 2

	BE vs. No BE			BE no dysplasia vs. BE w/dysplasia				
Confidence Level	0.95	0.95	0.95	0.95	0.95	0.95	0.95	0.95
Sensitivity	0.75	0.80	0.85	0.90	0.75	0.80	0.85	0.90
Confidence bands	0.085	0.078	0.070	0.059	0.105	0.097	0.087	0.073
N no BE/BE without dys/BE with dys	100	100	100	100	65	65	65	65

Statistical analysis

Phase 1: Tolerability score and level of mucosal abrasion will be summarized as median and interquartile range. Analysis of variance will be used to detect statistically significant differences in tolerability score and level of mucosal abrasion between different levels of sponge porosity and size. Failure/complication rate will be summarized as the percentage of the group total. Comparisons between sponge porosity and size for failure/complication rate will be analyzed using the Chi-squared test.

Phase 1 and 2: Marker specificity will be defined as the 90th percentile value in subjects without BE. Several markers will be combined based on the coefficients from a logistic regression model using subjects with BE vs subjects without BE as the response. This approach is used as they represent the broadest spectrum of disease and any marker combination that fails to discriminate between these two subgroups would not be of future value. The specificity of the combined markers will then be set equal to the 90th percentile in non-BE subjects. The corresponding sensitivity of individual markers as well as combined markers will be estimated with 95% confidence intervals.

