Marker specificity will be defined as the 90th percentile value in subjects with BE and no dysplasia. Several markers will be combined based on the coefficients from a logistic regression model using BE subjects with dysplasia vs subjects without dysplasia as the response. This approach is used as they represent the broadest spectrum of disease and any marker combination that fails to discriminate between these two subgroups would not be of future value. The specificity of the combined markers will then be set equal to the 90th percentile in BE subjects without dysplasia. The corresponding sensitivity of individual markers as well as combined markers will be estimated with 95% confidence intervals.

The association of demographic (age, gender, race), anthropometric (body mass index, waist hip ratio) and circulating biomarker levels (leptin, interleukins) with a BE diagnosis will be assessed using univariate and multivariable logistic regression analysis.

References:

- 5. Fitzgerald RC, di Pietro M, Ragunath K, et al. British Society of Gastroenterology guidelines on the diagnosis and management of Barrett's oesophagus. Gut 2014;63:7-42.
- 9. Phoa KN, van Vilsteren FG, Weusten BL, et al. Radiofrequency ablation vs endoscopic surveillance for patients with Barrett esophagus and low-grade dysplasia: a randomized clinical trial. JAMA 2014;311:1209-17.

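### Both marker panels are fitted, given their 90%-specificity cut-off and scored in the same subjects, with no internal validation and no estimate of specificity; Table 2 treats the cut-off as known

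*Combined protocol and SAP*

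**What the plan says.** The Statistical analysis section (Phase 1 and 2) treats the two panels alike.

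- BE against no BE: "Several markers will be combined based on the coefficients from a logistic regression model using subjects with BE vs subjects without BE", after which "The specificity of the combined markers will then be set equal to the 90th percentile in non-BE subjects".
- Dysplasia within BE: "Several markers will be combined based on the coefficients from a logistic regression model using BE subjects with dysplasia vs subjects without dysplasia", after which "The specificity of the combined markers will then be set equal to the 90th percentile in BE subjects without dysplasia".
- Output in both cases: "The corresponding sensitivity of individual markers as well as combined markers will be estimated with 95% confidence intervals".

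No estimate or interval for specificity is listed. The document does not mention cross-validation, bootstrap, optimism correction or a held-out set. It also does not say that a rule is locked in Phase 1 and tested in Phase 2.

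The first Phase 2 aim asks for both quantities: "Assess the sensitivity and specificity of a panel of DNA methylation markers in the nonendoscopic detection of BE". The second asks the same for dysplasia/carcinoma.

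The Phase 2 sample size text rests on the 95% interval for "sensitivity for detecting Barrett's Esophagus with a fixed specificity of 90" percent. It states half-widths under ±9% for BE and under ±12 for dysplasia, taken from Table 2. It also plans machine learning on at least 14 markers, sized by a "rule of thumb for machine learning of 10-15 events per marker", which gives 140 to 210 cases and as many controls. The plan does not say how many markers enter each logistic model, or whether they are chosen beforehand or in these data.

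**The concern.** Coefficients chosen to separate these subjects separate them better than they will separate the next ones. A cut-off that passes exactly 90% of these controls will pass fewer new controls. The reported sensitivity is then paired with a specificity that the rule does not achieve outside the study sample. Because 90% is set by construction, nothing in the planned output would show the shortfall, and half of each of the first two Phase 2 aims goes unanswered.

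There is a second, separate matter. The precision that justifies the sample size is for sensitivity at 90% specificity. That target depends on a cut-off estimated from a limited number of controls, and Table 2 appears to carry no allowance for this.

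**Working it through.** **1. Reproduce Table 2.** Inputs from the table: sensitivity p = 0.75, 0.80, 0.85, 0.90; n = 100 (BE) or 65 (dysplasia). Formula: 1.96·√(p(1−p)/n).

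- n = 100: 0.0849, 0.0784, 0.0700, 0.0588 (stated 0.085, 0.078, 0.070, 0.059).
- n = 65: 0.1053, 0.0972, 0.0868, 0.0729 (stated 0.105, 0.097, 0.087, 0.073).

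All eight match. Only binomial error in the cases is counted; the cut-off is treated as known.

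**2. Add the cut-off's sampling error.** Assumption: one fixed score, normal with equal variance in both groups, n per group. Variance = p(1−p)/n + r²·0.09/n, where r is the ratio of case to control density at the cut-off.

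- p = 0.75: the cut-off is at 1.28 and r = 0.318/0.1755 = 1.81. At n = 100 the variance is 0.001875 + 0.00295 = 0.00483, so the half-width is 1.96·0.0695 = 0.136. At n = 65 it is 0.169.
- p = 0.90: r = 1.00, giving 0.083 (n = 100) and 0.103 (n = 65).

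| Sensitivity | n = 100 (stated: under ±9) | n = 65 (stated: under ±12) |
|---|---|---|
| 75% | ±13.6 | ±16.9 |
| 80% | ±12.2 | ±15.2 |
| 85% | ±10.5 | ±13.0 |
| 90% | ±8.3 | ±10.3 |

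Direct simulation at 75% gives ±13.3 and ±16.1, so these are approximate. At 140 and 210 per group the formula gives about ±11.5 and ±9.4.

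**3. Specificity behind a nominal 90%.** For one fixed continuous marker with the cut-off at the k-th ordered control, true specificity follows Beta(k, n+1−k). With k = 90 of 100 the 95% range is 82-94%; with k = 59 of 65 it is 81-96%. This needs no assumption about the shape of the marker distribution.

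**4. Optimism of the fitted panel.** Simulation with 1000-2000 replicates: normal markers, error-free reference, equal groups, nearly unpenalised logistic fit, cut-off at the 90th percentile of the fitted controls. The ideal combination reaches 80% sensitivity at 90% specificity (separation 1.28 + 0.84 = 2.12 SD). In the 14-marker case, 3 are informative.

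| Panel, n per group | Apparent sensitivity | Same rule, new patients: sensitivity / specificity | Sensitivity at true 90% specificity |
|---|---|---|---|
| 14 fitted, 140 | 83.3% | 80.8% / 87.0% | 76.8% |
| 14 fitted, 210 | 82.1% | 80.5% / 88.0% | 77.9% |
| 4 fitted, 65 | 81.8% | 80.7% / 87.8% | 78.4% |
| 6 fitted, 65 | 82.8% | 80.9% / 86.9% | 77.3% |
| 3 pre-chosen, 140 | 80.6% | 80.2% / 89.2% | 79.5% |
| 4 pre-chosen, 140 | 81.1% | 80.6% / 88.8% | 79.3% |
| 3 pre-chosen, 210 | 80.5% | 80.2% / 89.4% | 79.7% |
| 4 pre-chosen, 210 | 80.5% | 80.2% / 89.3% | 79.5% |

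The 4-6 markers at 65 per group are what the plan's own rule allows: 65/15 = 4.3 and 65/10 = 6.5. For a single fixed marker the gap is under 1 point.

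**5. Binomial interval coverage, by target (n = 65 / 140 / 210).**

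- Sensitivity at a true 90% specificity: single marker 80 / 80 / 80%; 3 pre-chosen 73 / 77 / 78%; 14 fitted at 140 / 210, 46 / 54%.
- Sensitivity of the cut-off actually adopted: single marker 93 / 94 / 94%; 3 pre-chosen 92 / 95 / 95%; 14 fitted at 140 / 210, 82 / 89%.

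**6. Imperfect reference for dysplasia.** The sample size text assumes 30% undetected dysplasia among surveillance-negative BE subjects. Those subjects sit in the group whose top tenth defines the cut-off, so they push it up. The step 4 model was repeated with 30% hidden dysplasia carrying full or half the marker signal (an assumption). Apparent sensitivity is 39-67% and specificity against true status 98.7-94.6% (4 markers, 65 per group), or 42-69% and 98.3-93.7% (14 markers, 140 per group). Optimism against the same endoscopic labels remains, at 1-6 points.

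**7. Does validation recover the truth?** With 14 markers at 140 per group (150-200 replicates), the true new-patient values are 81.0% / 86.9%. Ten-fold cross-validation gives 81.1% / 86.8%, and bootstrap optimism correction 81.3% / 87.1%.

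**The case against.** The plan calls this an initial feasibility study and says that a combination which fails here would have no future value. That reads as screening for later work, where apparent accuracy is acceptable if labelled as such. Fixing specificity and reporting sensitivity is a recognised summary. The Preliminary Data report a three-marker dysplasia set and the Biomarker assays section names four BE markers, both from earlier work, so small panels are a fair reading. For those the bias at 140-210 per group is 1-2 points. All of this stands as a limit on size. But neither set is said to be locked, coefficients and cut-offs are still refitted here, and in-sample figures are not labelled apparent.

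The events-per-marker rule limits overfitting but does not measure it. The latent class, Bayesian and discrepant-resolution analyses address the imperfect reference, not optimism.

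Several stronger readings are tempting and are not supported:

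- *Dysplasia accuracy is overstated against true disease.* Under the plan's own 30% figure, sensitivity may be understated and specificity may exceed 90%.
- *Fourteen markers will be fitted at 65 per group.* That is 65/14 = 4.6 events per marker and breaks the plan's own rule.
- *Markers will be selected in these patients.* The plan does not say so.
- *Table 2 is miscalculated.* It is correct for a known cut-off.
- *The final intervals will be too narrow.* Their method is unstated. For a single marker or pre-chosen panel, binomial intervals for the adopted cut-off are near nominal.

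**Conclusion.** The point holds in limited form. Both panels are derived and scored in the same subjects without validation, and specificity is an aim that is never estimated. Neither statement depends on a simulation.

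Against new patients given the same labels, apparent sensitivity is too high and specificity is below 90%. For 14 fitted markers at 140-210 per group, the gap to sensitivity at a true 90% specificity is about 4-6.5 points. For 4-6 markers at 65 per group it is about 3-5.5. It is 1-2 for pre-chosen panels of 3-4 markers at 140-210, and under 1 for single markers. These sizes rest on normal markers, an error-free reference and 80% achievable sensitivity. For dysplasia the direction applies to endoscopic labels only.

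For the target that the sample size text names, Table 2's limits fail at assumed sensitivities of 75-85% and hold at 90%, under the equal-variance binormal assumption. The recalculated half-widths are approximations.

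**What to change.** In the Statistical analysis section:

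1. State how many markers enter each model and whether they are pre-chosen.
2. Make the main combined-panel estimates internally validated, by repeated 10-fold cross-validation or bootstrap optimism correction. Every resample should repeat any marker selection, the coefficient fit and the 90th-percentile cut-off.
3. Report validated sensitivity and specificity together, with bootstrap intervals that resample cases and controls. Label in-sample figures as apparent.
4. Use the same joint bootstrap for single-marker sensitivity at 90% specificity.
5. For the dysplasia panel, state that validated figures are against endoscopic labels, and present them beside the planned reference-standard analyses.

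In the Phase 2 sample size text and Table 2, either say that the half-widths are conditional on a known cut-off, or restate them with cut-off uncertainty as approximate figures with their assumptions.

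The cost is wording and computing time, with no added patients or procedures. Estimates become somewhat less favourable: about 2 points of sensitivity and 2-3 of specificity for 14 markers at 140-210 per group. Stated intervals widen. At 75% sensitivity they still exceed ±9 points at 140-210 per group (about ±11.5 to ±9.4), so that claim would have to be relaxed or tied to larger enrolment within the planned ceiling of 1000.

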Participants: Patients with and without known BE will be recruited from the Esophageal, Barrett's esophagus and general gastroenterology clinics in Mayo Clinic, Rochester (Phase I and 2), Mayo Clinic Health Systems – Austin, Mayo Clinic Health Systems – Mankato, Mayo Clinic Florida, Mayo Clinic Arizona, Northwell Health, and Baylor University Medical Center,. (Phase 2 only). Patients with known BE will be recruited to enrich the sample with BE subjects and those with BE related dysplasia/carcinoma. Potential cases declining to participate in the capsule sponge procedure or those not eligible due to exclusion criteria b.3. below will have the option to participate in the esophageal brushings portion of the study.

Inclusion criteria:

- a. Subjects with known BE.
 - 1. Patient between the ages 18 90.
 - 2. Patients with a BE segment ≥ 1cm in maximal extent endoscopically.
 - 3. Histology showing evidence of intestinal metaplasia with or without presence of dysplasia.
 - 4. Undergoing clinically indicated endoscopy.
- b. Subjects without known evidence of BE
 - 1. Undergoing clinically indicated diagnostic endoscopy.

Exclusion criteria:

- a. Subjects with known BE.
 - 1. Patients with prior history of ablation (photodynamic therapy, radiofrequency ablation, cryotherapy, argon plasma coagulation). *Patients with history of endoscopic mucosal resection alone will not be excluded.*
 - 2. Patients with history of esophageal resection for esophageal carcinoma.
- b. Subjects with or without known evidence of BE (on history or review of medical records).
 - 1. Pregnant or lactating females.
 - 2. Patients who are unable to consent.
 - 3. Patients with current history of uninvestigated dysphagia (this does not apply to the brushings only portion of the study).
 - 4. History of eosinophilic esophagitis, achalasia.
 - 5. Patients on oral anticoagulation including Coumadin, Warfarin.

- 6. Patients on antiplatelet agents including Clopidogrel, unless discontinued for at least three days prior to the sponge procedure.
- 7. Patients on oral thrombin inhibitors including Dabigatran and oral factor X a inhibitors such as rivaroxaban, apixaban and edoxaban, unless discontinued for at least three days prior to the sponge procedure.
- 8. Patients with history of known varices or cirrhosis.
- 9. Patients with history of esophageal resection for esophageal carcinoma.
- 10. Patients with congenital or acquired bleeding diatheses.

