- 11. Patients with a history of esophageal squamous dysplasia.
- 12. Patient has known carcinoma of the foregut (pancreatic, bile duct, ampullary, stomach, or duodenum) within 5 years prior to study enrollment.

Study procedures:

Participants will report fasting for ≥ 6 hours for the study.

A. Pre-procedure assessment:

- a. Baseline height, weight, hip, and waist circumference will be measured by the research coordinator.
- A validated questionnaire assessing reflux symptoms (RSQ) will be completed by the subject.
- c. At the Mayo Clinic sites only, 10 ml of blood will be obtained via venipuncture for measurement of circulating biomarkers (cytokines, adipokines and methylated DNA markers) of BE risk. Blood will be processed and separated into serum, plasma, and buffy coat for subsequent analysis for BE biomarkers.

Figure 1:25 mm sponge, intact and expanded

- d. Pregnancy test will be obtained for women of child bearing potential.
- B. Capsule sponge assessment:

For phase 1 subjects will be randomized using concealed allocation to one of two capsule sponges: 25 mm 10 ppi, 25 mm 20 ppi. All phase 2 subjects will receive the same single size and porosity sponge (porosity to be determined after analysis of Phase 1).

 Participants will be seated upright and asked to swallow the capsule sponge to which they have been randomized to, with

Figure 2: 30 mm sponge, intact and expanded

sips of water. The pharynx will then be anesthetized with Benzocaine 20% aerosol

- spray (Topex). After an interval of 5-10 min, the capsule sponge will be pulled out using steady traction using the string attached to the capsule sponge. As detailed in another Mayo IRB approved protocol (IRB 11-006429). The sponge will then be placed in a preservative solution and transferred to the laboratory for storage and subsequent analysis.
- b. Following completion of the capsule sponge study participants will fill out a tolerability questionnaire which allows patients to grade of discomfort during the procedure on a Likert scale of 0-10. 10 representing the "worst experience" and 0 the "best experience." This scale allows a comprehensive and individual assessment of the degree of pain, choking, gagging, and anxiety experienced during the procedure. Participants will also be asked if they would have the procedure again (yes/no).

C. Endoscopic assessment:

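### The exploratory Aim 4 risk-factor models pool seven sites with no site term, so their odds ratios are confounded if BE share and a factor's distribution vary by site in a related way

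*Combined protocol and SAP*

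**What the plan says.** Phase 2 Aim 4 is to "Explore the utility of demographic, anthropometric and circulating biomarker risk factors in predicting the presence of BE and BE related dysplasia". The matching analysis is one sentence at the end of Statistical analysis. It names the factors, "The association of demographic (age, gender, race), anthropometric (body mass index, waist hip ratio) and circulating biomarker levels (leptin, interleukins", and says that their association "with a BE diagnosis will be assessed using univariate and multivariable logistic regression analysis". It states no significance level, and recruiting site is not among the named variables. No stratified, conditional or random-effects model appears elsewhere in the document.

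Phase 2 is multicentre: "In addition to Mayo Clinic Rochester, subjects will also be recruited at Mayo Clinic Jacksonville; Mayo Clinic Arizona", followed by two Mayo Clinic Health Systems sites, one site in New York and one in Texas. That makes seven recruiting sites. For an eighth, "Enrollment is closed at University of Colorado, Denver".

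Under Participants, "Patients with known BE will be recruited to enrich the sample with BE subjects and those with BE related dysplasia/carcinoma". The sole inclusion criterion listed for subjects without known BE is "Undergoing clinically indicated diagnostic endoscopy". No ratio or quota of cases to controls is set by site, and controls are not matched to cases.

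Under Pre-procedure assessment, "At the Mayo Clinic sites only, 10 ml of blood will be obtained via venipuncture for measurement of circulating biomarkers". Any model containing leptin or an interleukin therefore draws on five of the seven recruiting sites.

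**The concern.** The proportion of participants with BE at a site depends partly on how many known cases that site enrols, and nothing in the plan equalises it. Age, race and body size may also differ between sites in Minnesota, Florida, Arizona, New York and Texas. If sites with a higher BE share also tend to have, say, older participants, a pooled model attributes that site difference to age, even if age and BE are unrelated within every site.

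The five-site and seven-site samples add a second difficulty. A coefficient could change between a univariate model on seven sites and a multivariable model with blood markers on five, simply because the site mix has changed.

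What is at stake is which factors are reported as associated with BE. A variable that only marks the recruiting site could be carried forward as a predictor.

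**Working it through.** **The nearest figure in the plan.** Aim 4 has no sample size of its own. The Phase 2 minimum for modelling methylation markers reproduces: 14 × 10 = 140 and 14 × 15 = 210 cases; doubled, 280 and 420 participants. Planned enrolment is up to 1000. I use 280, 420 and 1000. The 5% two-sided level is an assumption, because the plan states one only for Phase 1. Every by-site input below is also an assumption.

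**Two equal sites, binary factor, within-site odds ratio 1.0.** Let the BE share be 70% and 30%, and factor prevalence 60% and 40%.
- Prevalence in cases: 0.7 × 0.6 + 0.3 × 0.4 = 0.54.
- Prevalence in controls: 0.3 × 0.6 + 0.7 × 0.4 = 0.46.
- Pooled odds ratio: (0.54/0.46) ÷ (0.46/0.54) = (0.54/0.46)² = 1.38.
- At N = 280 (140 cases, 140 controls) the cells are 75.6, 64.4, 64.4 and 75.6. The standard error of the log odds ratio is √(2/75.6 + 2/64.4) = 0.240, and z = 0.321/0.240 = 1.34. The rejection rate is 27%; it is 37% at N = 420 and 71% at N = 1000.

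With milder differences (BE share 60% and 40%, prevalence 50% and 40%), prevalence is 0.46 in cases and 0.44 in controls. The pooled odds ratio is (0.46/0.54) ÷ (0.44/0.56) = 1.08, and rejection is 6% to 10% from N = 280 to 1000.

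**Two equal sites, continuous factor.** The case-control gap is the difference in BE share times the site shift in SD units, and the odds ratio per SD is roughly exp(gap).
- 70/30 with a 0.3 SD shift: 0.4 × 0.3 = 0.12, odds ratio about 1.13. Simulated rejection is 17% (N = 280) and 22% (N = 420).
- 60/40 with a 0.2 SD shift: 0.2 × 0.2 = 0.04, odds ratio about 1.04. Simulated rejection is 6–7%.

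**Seven sites, simulated.** There were 1000 runs per setting and a Wald test. Half of participants were cases, there was no within-site association, and site sizes were 40%, 12%, 12%, 8%, 8%, 10% and 10%. Simulation error is √(0.05 × 0.95/1000) = 0.7 points. In the table, BE share and factor mean are correlated across sites at about 0.72. The spread columns are SDs across sites, and the odds ratio is per within-site SD.

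| BE-share spread | Factor spread | Spurious OR | N = 280 | N = 420 | N = 1000 |
|---|---|---|---|---|---|
| 10 points | 0.2 SD | 1.06 | 6.1% | 8.9% | 14.9% |
| 15 points | 0.3 SD | 1.13 | 17.4% | 23.0% | 48.9% |
| 20 points | 0.4 SD | 1.22 | 39.9% | 59.2% | 92.7% |

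As a check on the middle row, the expected gap is 0.72 × 0.15 × 0.3 ÷ 0.25 = 0.13 SD, in line with an odds ratio of 1.13.

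Three further results bound the claim:
- When only the BE share varies (15 points) or only the factor varies (0.3 SD), rejection without a site term is 3.8–5.3%. There is no inflation.
- When the two site patterns are aligned at random in each run, rejection from N = 280 to N = 1000 is 6.4–10.8%, 12.4–34.9% and 28.8–61.1% for the three spreads. With seven sites, chance alone often produces some alignment.
- With site indicators in the model, rejection is 3.7–6.4% in every seven-site setting.

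**The case against.** Several points on the other side stand.

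- A reader might infer that enrichment itself biases these models. It does not: sampling on the outcome leaves a logistic odds ratio valid, and the results above show no inflation when only the BE share varies.
- A reader might also infer that cases come from Barrett's clinics and controls from general gastroenterology. Participants says that both groups are recruited from the same three types of clinic, and it gives no split by clinic or site.
- The plan is silent on site; it does not exclude it. The named list gives the exposures of interest, and a multivariable model could also carry a site term. The univariate models, as named, could not.
- Aim 4 is exploratory and has no significance level or decision rule, so the rejection rates describe how results may be read, not an error rate the plan promises to control. The 280 to 420 range sizes the methylation-marker work.
- The spurious odds ratios are modest in most settings, and all rest on assumed inputs.
- Site adjustment removes site confounding only. Any difference in how cases and controls are selected within a site remains.

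These points limit the claim and its priority. They do not supply the missing provision: the analysis sentence names no handling of site, and the design leaves BE share free to vary across seven locations.

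**Conclusion.** The point holds in conditional form. The pooled Aim 4 odds ratios are open to confounding by site, and they are confounded if BE share and a factor's distribution vary across sites in a related way. Whether they do, and by how much, cannot be determined from the documents. Over the assumed range the spurious odds ratio is about 1.04 to 1.4. The false-positive rate is near nominal for modest differences and far above it for wide ones. It grows with sample size, so enrolling towards 1000 makes a spurious association easier to declare, not harder.

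The documents do not support extending this to the sensitivity, specificity or missed-dysplasia aims. Nor do they show that blood handling differs between sites or that a real factor would be masked; neither was calculated. This is an inexpensive improvement to an exploratory analysis, not a flaw in the trial's main estimates.

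**What to change.** Add to the last paragraph of Statistical analysis, in substance: all univariate and multivariable risk-factor association models will include recruiting site as a fixed effect, with small sites grouped by a rule stated in advance; models with circulating markers will be adjusted over the Mayo sites that draw blood; BE and non-BE counts will be tabulated by site. If the closed site contributed participants to the analysis, it should be a level of the site variable too. Unadjusted results may be shown alongside.

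The cost is at most 7 − 1 = 6 degrees of freedom for the seven recruiting sites (one more if the closed site is a separate level), or 5 − 1 = 4 for the blood-marker models, and fewer after grouping. A site with only cases or only controls adds no information to the adjusted estimate; grouping lessens that loss. Recruiting site is known for every participant, so no new data or procedure is needed. Stating the adjustment in advance also avoids a later choice between adjusted and unadjusted results.
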